2.3.2 Treatment Assignment and Randomization Procedures

Cohorts

Number	Name	Description
1	Cohort 1	Patients with HCL with (62 patients) and without (68 subjects) prior course of purine analog to be randomized between Arm 1 and Arm 2 (randomization stratified based upon prior purine analog [yes/no])
2	Cohort 2	Patients with HCL without prior course of purine analog to be directly assigned to Arm 3 (25 patients; after completion of the 68 patients without prior purine analog in Cohort 1)
3	Cohort 3	Patients with HCLv to be directly assigned to Arm 3 (20 patients)

Arms

Number	Name	Description
1	Arm 1	Cladribine + Rituximab
2	Arm 2	Cladribine (+ Rituximab after 6 months if MRD detected)
3	Arm 3	Cladribine + Rituximab (Rituximab will be administered just before rather than after the 1 st of the 5 daily doses of cladribine on day 1)

Stratifications

Name	Distinct Options	Notes

Prior purine analog	Yes No	Applies to Cohort 1 patients randomized between Arm 1 and Arm 2 only (see below).
---------------------	-----------	---

Randomization and Arm Assignment

At the time of registration, patients in Cohort 1 will be randomized between Arm 1 and Arm 2, and patients in Cohort 2 will be directly assigned to Arm 3. Patients with variant HCL (HCLv; Cohort 3) regardless of prior treatment with purine analog are assigned to Arm 3.

- Cohort 1: HCL Patients will be randomized between Arm 1 and 2. Randomization will be stratified on the basis of prior purine analog or not. There will be 68 patients randomized within the no prior purine analog stratum and 62 randomized within the 1+ prior purine analog stratum.
 - Note: The randomization for Cohort 1 will be performed by CRO personnel using randomization assignments generated by the study statistician. The Pharmacy Department will be notified of the treatment assignment once the patient is randomized.
- Cohort 2: 25 patients with no prior purine analog will be assigned directly to Arm 3 following completion of randomization of the 68 patients in the ‘no prior purine analog’ stratum in Cohort 1.
- Cohort 3: Patients with variant HCL (HCLv) regardless of prior treatment with purine analog will be enrolled in this cohort, will not be randomized and will be assigned to Arm 3.

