Patients enrolled on this trial may have received 0 prior cycles of purine analog or 1 prior cycle of purine analog. Data from previous studies suggests that patients without prior purine analog exposure have a higher complete response rate when they receive cladribine (91%, with a median CR duration of 53 months) compared to those with 1 prior cycle of cladribine, who have a CR rate of 62% (along with 26% PRs) and an associated response duration of 23 months. As a result, since MRD and development of a complete response are inter-related, the levels of MRD found may quite possibly differ according to whether the patients have received previous cladribine or not. Patients will be assigned to cohorts (Cohorts 1 and 2) according to whether they have received prior purine analog or not. In addition, the study will be designed to have adequate numbers of subjects in each category (prior purine analog exposure or not) in order to ensure reasonable interpretation for each of the two strata.

The goal will be to randomize a total of 68 evaluable patients with 0 and 62 with 1 prior courses of purine analog at the time of starting cladribine on this trial. MRD evaluations will be performed every month for 3 months after treatment initiation, every 3 months for 2 years, and every 6 months thereafter. The evaluation made nearest to 6 months after cladribine will be considered the primary evaluation and may vary +/- 2 weeks (i.e. done at or 24-28 weeks) due to scheduling or drug administration. With 34 randomized patients in each arm of the group with no prior purine analog, there will be 80% power to detect a difference in MRD rates of 5% vs. 25% 6 months after cladribine with or without rituximab, respectively, a 20% difference, using a Fisher's exact test with a 0.1 one-sided significance level. With 31 randomized patients in each arm of the group with 1 prior course of purine analog, there will be 80% power to detect a difference in MRD rates of 10% vs. 35% 6 months after cladribine with or without rituximab, respectively, a 25% difference. Differences will also be explored using the other tests of MRD, including marrow and blood consensus PCR and RQ-PCR.

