6.2 SECONDARY ENDPOINTS

In addition to the primary goal of determining differences in the MRD level according to rituximab administration, the following goals will also be explored in patients on this study.

The most important secondary endpoints are MRD-free survival after cladribine, and MRD-free survival after up to 2 courses of rituximab. For the secondary endpoints of this protocol, and for triggering delayed rituximab, patients with or without CR are considered MRD+ if the blood FACS is positive or if low blood counts become inconsistent with CR (ANC < 1500/ μ l, Plt < 100,000/ μ l, or Hgb < 11). Patients FACS-negative in both blood and bone marrow aspirate are considered MRD-negative regardless of blood counts. Failure of cladribine and/or rituximab to clear MRD by blood FACS requires that this test be positive at 6 months since MRD at 1-3 months may clear by 6 months. However, MRD relapse will be considered when first detected, even if before 6 months, if cladribine and/or rituximab fail to clear MRD at 6 months. If simultaneous cladribine and rituximab is superior to cladribine and delayed rituximab, MRD-free survival after cladribine and after delayed rituximab should together be longer if cladribine was combined with rituximab than if used alone. In order to compare the probability of development of MRD as a function of time according to whether rituximab is used immediately or not, Kaplan-Meier curves for this endpoint will be created, beginning at the date of randomization, and compared using a two-tailed log-rank test. Patients who develop MRD will be considered to have had an event for the actuarial curve, while those without MRD found in this manner will be considered censored and will remain in follow-up for this endpoint. With each stratum considered separately, or if both strata are combined, the power for this comparison will potentially be low, but the results may demonstrate a trend if one is present. Measurement of best response to cladribine vs. cladribine + rituximab will also be done at 1 and 6 months after cladribine. The CR and PR rates will be reported, as well as appropriate 95% exact confidence intervals.

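### Section 6.2 does not say that a combined-strata log-rank test of MRD-free survival is stratified by prior purine analog, the factor used to stratify randomization

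*Combined protocol and SAP*

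**What the plan says.** **Design.** Section 2.3.2 says of Cohort 1: "Randomization will be stratified on the basis of prior purine analog or not". Section 6.1 sets the numbers: "The goal will be to randomize a total of 68 evaluable patients with 0 and 62 with 1 prior courses of purine analog". That gives 34 per arm and 31 per arm.

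**Expected prognosis.** Section 1.3.4 separates the groups before randomization because their historical CR rates were 91% and 62%. Section 6.1 adds durations. For patients without prior treatment it gives "91%, with a median CR duration of 53 months"; patients with one prior cycle are those "who have a CR rate of 62% (along with 26% PRs) and an associated response duration of 23 months". It infers that MRD levels may differ by stratum too, without giving a size.

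**Analysis.** Section 6.2 plans Kaplan-Meier curves from randomization, "compared using a two-tailed log-rank test". It allows for looking at the strata separately or together: "With each stratum considered separately, or if both strata are combined, the power for this comparison will potentially be low". It gives no significance level, hazard ratio, event count or follow-up length for this test. Neither a stratified log-rank test nor a Cox model is mentioned anywhere.

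**Status.** Section 1.3.2 calls blood MRD-free survival the major secondary endpoint. Section 6.2 describes everything other than the 6-month MRD comparison as exploratory.

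**The concern.** When a trial stratifies randomization on a factor expected to predict outcome, the pooled test should normally condition on that factor. A plain log-rank test puts good- and poor-prognosis patients in the same risk sets. The poor-prognosis patients leave first, so the mix changes over time, the marginal treatment effect is pulled towards no difference, and the variance estimate does not credit the balance that stratified randomization provides.

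The endpoint matters. Section 1.3.2 says a 6-month MRD difference would not by itself show that simultaneous rituximab gives a better clinical outcome, and it looks to MRD-free survival for that. With at most 130 randomized patients and power already expected to be low, efficiency should not be given away. The silence also leaves two versions of the pooled test open after the data are seen, and they can fall on opposite sides of a significance threshold.

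**Working it through.** **1. The plan's own power figures.** These are for the primary Fisher's exact test at one-sided 0.1. Exact enumeration gives 80.6% for 34 per arm (5% v 25%) and 80.3% for 31 per arm (10% v 35%), against the stated 80%. They reproduce. There is no stated power for the log-rank test to reproduce.

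**2. Inputs for the log-rank comparison.**
- From the documents: 34 + 34 and 31 + 31 patients; stratification by prior purine analog; historical durations of 53 and 23 months; control MRD rates at 6 months of 25% and 35%. The rates follow Section 6.1. Section 1.3.5 attaches 10% and 35% to the arms the other way round.
- Assumed: two-sided alpha 0.05, exponential times, a common hazard ratio (HR) of 0.5 to 0.7 in both strata, and follow-up of 24 months for all, uniform over 12-96 months, or uniform over 60-180 months.

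**3. Two versions of the gap between strata.**
- Wide: control medians of 53 and 23 months, a hazard ratio between strata of 53/23 = 2.3.
- Narrow: medians implied by the control MRD rates, using median = 6 × ln 2 / (−ln(1 − rate)). For 25%: 4.159/0.2877 = 14.5 months. For 35%: 4.159/0.4308 = 9.7 months. The hazard ratio between strata is 1.5.

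**4. Tests compared.** With U = sum of (observed − expected) events in one arm and V its variance:
- Plain: Z = U/√V, with all 130 patients in one risk set.
- Stratified: Z = (U₀ + U₁)/√(V₀ + V₁), computed within each stratum and then added.

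**5. Simulated power, plain → stratified** (20,000 trials per cell).

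| Gap | HR | 24 months | 12-96 months | 60-180 months |
|---|---|---|---|---|
| Wide | 0.7 | 19.9% → 21.6% | 27.6% → 31.5% | 36.6% → 43.9% |
| Wide | 0.6 | 34.6% → 36.9% | 49.8% → 54.8% | 65.1% → 72.2% |
| Wide | 0.5 | 54.8% → 57.1% | 75.0% → 78.8% | 89.1% → 92.7% |
| Narrow | 0.7 | 37.6% → 38.7% | 44.3% → 45.7% | 48.7% → 50.5% |
| Narrow | 0.6 | 64.3% → 65.4% | 72.9% → 73.8% | 79.1% → 80.3% |
| Narrow | 0.5 | 86.7% → 87.3% | 93.4% → 93.9% | 96.4% → 96.7% |

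The gain is 1.7 to 7.3 points with the wide gap and 0.3 to 1.8 points with the narrow one.

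**6. Type I error.** With the wide gap and no treatment effect, the plain test rejects in about 3.8-4.2% of trials at nominal 5%, and the stratified test in about 4.7-5.5%. The plain test errs on the safe side.

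**7. What the gain is worth.** At HR 0.6 with the wide gap, the equivalent increase in events is ((1.96 + z of stratified power)/(1.96 + z of plain power))². For 24 months: (1.626/1.564)² = 1.08. For 12-96 months: (2.081/1.955)² = 1.13. For 60-180 months: (2.549/2.348)² = 1.18. That is 8%, 13% and 18% more events.

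**8. What it does not buy.** Events for 80% power by Schoenfeld's formula are D = 4(1.960 + 0.842)²/(ln HR)². At HR 0.6 this is 31.4/0.261, or 121 events. The wide-gap simulations yield about 42, 69 and 103 events for the three follow-up patterns, so the shortfall in events remains.

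**The case against.** **The plan is silent, not wrong.** A reader might infer that the plan ignores the stratification factor or commits to an unstratified test. The text does not support that: it does not describe how the strata would be combined, and a stratified log-rank test is one way to do it. The design also allows for conclusions by stratum (Section 1.3.4), and 6.2 mentions separate analysis first. This stands. The point is an omission about the pooled analysis only.

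**The gap between strata may be small for this endpoint.** A reader might infer very different MRD-free survival from 53 v 23 months. Those are response durations from earlier studies. For MRD itself the plan says only that levels may differ, and its control rates are 25% and 35%. This also stands, and it is why the gain is given as two ranges.

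**The hazard ratios are not the plan's.** If the 6-month targets reflected sustained exponential effects, they would imply hazard ratios of ln 0.95/ln 0.75 = 0.18 and ln 0.90/ln 0.65 = 0.24. Either test would then have ample power: with medians of 53 and 23 months and 24 months' follow-up, 97.0% plain v 97.3% stratified. That is fair, but 6.2 itself expects low power, which fits more moderate effects.

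**The comparison is exploratory and its low power is disclosed.** True, and this limits the weight of the point. It is not a reason to leave the less efficient test open when the better one is free.

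**Conclusion.** The point holds as a free improvement. Section 6.2 leaves unstated whether a combined-strata log-rank test is stratified by prior purine analog. If it is not, the test is slightly conservative and loses about 2 to 7 points of power at hazard ratios of 0.5 to 0.7 when the strata differ as the historical durations do, or about 0 to 2 points when they differ only as the planned control MRD rates do. These sizes rest on the assumed hazard ratios, follow-up, exponential times, common effect across strata and two-sided alpha of 0.05; the documents give none of these for this test.

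Two stronger conclusions are not supported. A plain test would not inflate false positives here. Nor is the missing stratification the reason power is low: the number of events drives that, and stratifying does not change it. The primary 6-month comparison is unaffected.

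**What to change.** Add one sentence to Section 6.2: any log-rank test that combines the two randomized strata will be stratified by prior purine analog (0 v 1), and any hazard ratio reported with it will be stratified in the same way. State the significance level used for that test. Keep the separate-stratum analyses as planned. No Cox model needs to be added; the hazard-ratio clause applies only if one is reported.

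The cost is the wording alone. It needs no extra patients, visits or data, because prior purine analog is already recorded for randomization. The sentence should be in place before the arms are compared on this endpoint.

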6.3 ADDITIONAL CONSIDERATIONS

6.3.1 Additional non-randomized 25-patient cohort receiving rituximab plus cladribine

An important secondary objective is to determine if combined cladribine and rituximab are feasible to administer as an outpatient. Enrollment of non-randomized patients to begin rituximab immediately prior to cladribine may facilitate outpatient administration by obviating the time needed for randomization. Also, changing the sequence of first doses of rituximab and cladribine to rituximab first may avoid rapid thrombocytopenia, which could in some cases require inpatient treatment. It is important to verify, however, that the new sequence is non-inferior with respect to the primary endpoint, MRD at 6 mo after cladribine. If after enrolling 34 newly diagnosed HCL patients to immediate rituximab following cladribine, 1 has MRD (currently the number is 1 of 27), then the new 25-patient cohort receiving cladribine immediately after rituximab could be compared as follows: When the sample sizes in the groups are 34 and 25, a two-group test of proportions with a one-sided 0.050 significance level will have 84% power to reject the null hypothesis that the test and the standard are not equivalent (the difference in proportions, is 0.12 or farther from zero in the same direction) in favor of the alternative hypothesis that the proportions in the two groups are equivalent, assuming that there is no expected difference in proportions is 0.000 and the proportion in the standard group is 0.97. If 2 of 34 patients have MRD (proportion = 0.94), there would be 81% power to rule out a 16% difference.

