1.3.10 Simultaneous rituximab and cladribine as an outpatient

An important secondary objective is to determine if combined cladribine and rituximab are feasible to administer as an outpatient. Enrollment of non-randomized patients to begin rituximab immediately prior to cladribine may facilitate outpatient administration by obviating the time needed for randomization. Also, changing the sequence of first doses of rituximab and cladribine to rituximab first may avoid rapid thrombocytopenia, which could in some cases require inpatient treatment. A 25-patient cohort treated in nonrandomized fashion will permit >80% power to rule out a 12-16% decrease in MRD-free rate from that observed in the randomized newly diagnosed HCL patients receiving cladribine prior first dose of rituximab.

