3 STUDY IMPLEMENTATION

3.1 STUDY DESIGN

3.1.1 Overview

This is a randomized study of cladribine with or without rituximab in HCL, along with delayed rituximab for MRD relapse. The primary objective of the study is to determine if HCL MRD differs at 6 months after cladribine according to whether or not rituximab is administered concurrently with cladribine. MRD for the primary objective is defined as positive blood FACS, bone marrow aspirate FACS, or BMBX IHC.

Two groups, including 68 patients with HCL and no prior courses of purine analog and 62 with HCL and 1 prior course of purine analog (Cohort 1), will be randomized according to the following schema showing numbers of patients. Following enrollment of the first evaluable 68 patients with no prior purine analog, 25 additional patients will be enrolled into the Cohort 2 and they will all receive rituximab and cladribine without randomization. However, the first of the 8 weekly doses of rituximab will be administered just before rather than after the 1st of the 5 daily doses of cladribine on day 1. The goal of this 25-patient non-randomized group is 1) to enable combined treatment as an outpatient due to the time saved from not randomizing, and 2) to determine if rapid reversible thrombocytopenia can be avoided by beginning the rituximab immediately before the 1st dose of cladribine, rather than immediately afterward. If after 10 of these nonrandomized patients it is evident that toxicity is higher with rituximab begun before cladribine than afterward,

the remaining 15 nonrandomized patients will be enrolled, and treated as outpatients if possible, with the rituximab begun after the 1st dose of cladribine as in the randomized patients.

A third group will be enrolled and will contain 20 HCLv patients who will not be randomized and will receive rituximab concurrently with cladribine.

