Other secondary endpoints include determining disease-free and overall survival, MRD rates after cladribine and rituximab separately and combined, correlation of MRD rates and tumor markers with clinical endpoints and determining whether cladribine + rituximab can lead to long-term freedom from relapse of MRD or CR/PR, using MRD/tumor marker data to determine when bone marrow biopsy can be avoided in managing HCL, determining if rituximab benefit is different in patients receiving their 1st or 2nd course of purine analog, prospectively evaluating the effect of cladribine and rituximab on normal T- and B-lymphocytes, and studying HCL biology using monoclonal immunoglobulin sequences. When possible, blood will be drawn to obtain RNA for microarray analysis. This will be particularly important in contrasting patients with HCL and HCLv. Finally, to correlate bone marrow MRI signal with bone marrow biopsy, patients will obtain cervical and thoracic spine MRI at baseline and at bone marrow restaging time points, when feasible.

These secondary goals will be determined using appropriate actuarial methods as needed, along with descriptive analyses. Other than the comparisons identified as being of primary interest (comparison of MRD 6 months after starting trial), all of these evaluations will be done with exploratory intent and reported without formal adjustment.

As mentioned in Section 1.3.12 above, the CD25-variant of HCLv has a much poorer prognosis after cladribine than classic HCL and would create a bias if such patients are randomized. Therefore, patients will be initially grouped based on having HCLv vs. HCL, and the HCLv patients will receive concurrent cladribine and rituximab. The first 68 HCL patients with no prior

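### The 25-patient non-inferiority comparison cannot deliver both a one-sided 0.050 level and more than 80% power at 12-16 points

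*Combined protocol and SAP*

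**What the plan says.** Section 6.3.1 adds a cohort of 25 newly diagnosed patients who start rituximab just before cladribine. They are to be compared on 6-month MRD with the 34 newly diagnosed patients randomized to immediate rituximab after cladribine. On the purpose it says: "It is important to verify, however, that the new sequence is non-inferior with respect to the primary endpoint".

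On the operating characteristics it says that "a two-group test of proportions with a one-sided 0.050 significance level will have 84% power to reject the null hypothesis" of non-equivalence, and two scenarios are given, both with a true difference of zero:

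- 1 of 34 with MRD (MRD-free proportion 0.97), 12-point margin: 84% power.
- The second reads: "If 2 of 34 patients have MRD (proportion = 0.94), there would be 81% power to rule out a 16% difference".

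Section 1.3.10 uses the result to support the cohort size, saying that 25 patients "will permit >80% power to rule out a 12-16% decrease in MRD-free rate". No test statistic or interval method is named for this comparison. Section 6.2 says of everything other than the primary comparison that "all of these evaluations will be done with exploratory intent and reported without formal adjustment".

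**The concern.** The expected numbers of MRD-positive patients are very small: 34 × 0.03 = 1.0 and 25 × 0.03 = 0.75 in the first scenario, 34 × 0.06 = 2.0 and 25 × 0.06 = 1.5 in the second. A normal approximation to a difference in proportions is unreliable at such counts, and near 100% it errs towards declaring non-inferiority too easily. If so, the stated level and the stated power do not belong to the same test.

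Two things are at stake. The plan promises an assurance about the new sequence that the design may not give. And because the method is unnamed, one patient can decide whether non-inferiority is declared, depending on which method is chosen after the data are in.

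**Working it through.** **Inputs (section 6.3.1).** One-sided level 0.050; n₁ = 34 (cladribine first), n₂ = 25 (rituximab first); true difference 0. Scenario 1: MRD-free p = 0.97, margin d = 0.12. Scenario 2: p = 0.94, d = 0.16. The null points are therefore 0.97 vs 0.85 and 0.94 vs 0.78.

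**Step 1: reproduce the plan's figures.** Large-sample power = Φ( d / √[p(1−p)(1/34 + 1/25)] − 1.645 ).

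- Scenario 1: √(0.0291 × 0.06941) = 0.04494; 0.12/0.04494 = 2.670; Φ(1.025) = 84.7%.
- Scenario 2: √(0.0564 × 0.06941) = 0.06257; 0.16/0.06257 = 2.557; Φ(0.912) = 81.9%.

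A noncentral t with 57 degrees of freedom gives 84.0% and 81.1%, matching the stated 84% and 81%. The source is evidently a large-sample formula.

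**Step 2: enumerate all 35 × 26 outcomes.** For each test, the binomial probabilities of the outcomes that declare non-inferiority are summed, under (p, p) for power and under (p, p − d) for type I error at the design null.

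| Test | Power, scenario 1 | Type I error, scenario 1 | Power, scenario 2 | Type I error, scenario 2 |
|---|---|---|---|---|
| Large-sample (unpooled Wald) | 83.9% | 10.7% | 80.0% | 7.6% |
| Farrington-Manning score | 56.8% | 4.1% | 60.5% | 3.8% |
| Exact unconditional | 49.7% | 2.4% | 60.5% | 3.6% |

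Maximised over all null rates, the Wald test's error is 18.0% and 9.7%. The score test's is about 5.7% in both scenarios. The exact test's is at most 5%.

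**Step 3: why this happens.** In scenario 1 the number of MRD-positive patients among the 25 largely decides the result:

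- P(0 of 25) = 0.97²⁵ = 46.7% if the true MRD rate is 3%, so requiring zero cannot give 80% power.
- Allowing one raises this to 82.8%, but P(≤1 of 25) is already 9.3% when the true MRD rate is 15%, the value that should be ruled out.

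In scenario 2, allowing one gives 55.3% power and 1.6% error; allowing two gives 81.3% and 6.4%.

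**Step 4: does the result depend on the test chosen?** No. The Neyman-Pearson most powerful test of the design null against the design alternative bounds the power of every level-0.05 test. The bounds are 62.3% in scenario 1 and 73.7% in scenario 2.

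**Step 5: what could be ruled out with more than 80% power.** Smallest whole-point margin with type I error at or below 5% at the design null:

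- Score: 17 points at p = 0.97 (power 86.5%, error 4.9%); 20 points at p = 0.94 (power 82.6%, error 4.7%).
- Exact: 18 points at p = 0.97 (86.5%); 20 points at p = 0.94 (82.6%).

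**Step 6: can the verdict change?** Take 33/34 MRD-free in the randomized arm, 24/25 in the new cohort and a 12-point margin. The Wald z is 2.24 (pass) and its one-sided 95% lower bound is −9.1 points. The score z is 1.50 (fail) and its lower bound is −13.5 points; 25/25 would be needed (z = 2.08). With 32/34 and a 16-point margin, Wald accepts 23/25 (z = 2.05), while the score test does not (z = 1.61) and needs 24/25 (z = 2.10).

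**Step 7: the 10-patient rule.** Section 3.1.1 provides that, if toxicity proves higher after 10 patients, "the remaining 15 nonrandomized patients will be enrolled, and treated as outpatients if possible, with the rituximab begun after the 1st dose of cladribine". Only 10 patients would then have had the new sequence. Against 33/34 at 12 points, even 10/10 gives a score z of 1.32, so no result could pass. Against 32/34 at 16 points, only 10/10 passes (z = 1.66).

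**The case against.** The strongest reply is that the plan's arithmetic is right for a standard formula, that section 6.3.1 only says the cohort could be compared in this way, and that section 6.2 labels all non-primary evaluations exploratory. The cohort's stated goals in section 3.1.1 are outpatient treatment and avoiding thrombocytopenia, and no enrolment or treatment rule turns on this test. A sequential, non-randomized comparison also has sources of bias that no choice of test removes.

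Most of this is fair and limits the consequences. It does not make the stated level and power true. The formula was used outside the range where it holds, section 6.3.1 calls the verification important, and section 1.3.10 uses the power claim to support the cohort size.

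A second reply is that the margin is defined, since each one is tied to the randomized arm's MRD count. That holds only for counts of 1 and 2. Other counts are not covered, and the margin widens as the comparator does worse, which is not a margin fixed in advance.

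A third is that the score test itself slightly exceeds 5%. It does, by up to about 0.7 points at the stated margins and by a similar amount at 17 and 20 points. That is why the strictly exact alternative is given beside it.

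**Conclusion.** The point holds. With 34 and 25 patients, a one-sided 0.050 level and 84%/81% power at 12/16 points are not jointly attainable by any test. The procedure that matches the stated power has about 2 and 1.5 times the stated error at the design's own null points. A test that stays below 5% at those points has power of roughly 50-57% in the first scenario and about 60% in the second. No single margin is prespecified.

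These figures rest on independent binomial counts, the MRD-free rates stated in section 6.3.1, no true difference, and all 25 patients receiving rituximab first. That the plan used a large-sample formula is inferred from the match in step 1; the bound in step 4 does not depend on it. The primary randomized comparison is untouched. The point should be fixed, because the plan states a power that its design does not have.

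**What to change.** In sections 6.3.1 and 1.3.10:

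1. Name the method: a Farrington-Manning score test or an exact unconditional non-inferiority test. If the score test is chosen, note that its maximum error is slightly above 5%.
2. State one margin in advance, independent of the observed MRD count in the randomized arm.
3. Restate the power for the chosen method. At 12 points (0.97) it is 56.8% by score and 49.7% by exact test; at 16 points (0.94) it is 60.5% by either. If the claim of more than 80% power is kept, replace 12-16 points with 17-20 (score) or 18-20 (exact).
4. Add a sentence that the comparison uses only patients who received rituximab first, and that the power figures do not apply if the 10-patient rule in section 3.1.1 is invoked.

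A simpler alternative to items 1-3 is to report the difference with an exact confidence interval and drop the non-inferiority wording and power claim.

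The change is to text only and needs no more patients. The cost is a less favourable stated power or a wider margin.
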